7.2. Dose Selection Rationale

The dose of eteplirsen used in this study is 30 mg/kg. This dose was chosen based on results from the Phase 2, double-blind, placebo-controlled, multiple-dose study, Study 4658-us-201, and its open-label extension, Study 4658-us-202. As described in Section 5.3, these studies assessed the efficacy, safety, tolerability, and PK of 2 eteplirsen doses (50 and 30 mg/kg) administered as IV infusions in twelve 7- to 13-year-old pediatric patients diagnosed with DMD with out of frame mutations amenable to treatment by skipping exon 51.

Once weekly treatment with 30 mg/kg eteplirsen for 24 weeks significantly increased the mean percentage of dystrophin-positive muscle fibers as percent (%) of normal in DMD patients compared to placebo.

[figure not shown]
At Week 48, increases in the percent of dystrophin-positive fibers were similar for patients who had received weekly 30 and 50 mg/kg eteplirsen without interruption from Week 1 (52% and 42% of normal, respectively or 47% for the combined groups). These data suggest that the effect of eteplirsen on the production of novel dystrophin is not significantly different between the two doses tested in this study. Therefore, the lower dose was selected as the more conservative choice, because patients presumably would receive this drug as a life-long treatment.

7.3. Study Endpoints

7.3.1. Safety Endpoints

Incidence of:

- Adverse events
- Clinical laboratory abnormalities
- Abnormalities in vital signs and physical examinations
- Abnormalities on electrocardiograms (ECGs) and echocardiograms (ECHO)

7.4. Discussion of Study Design

This is an open-label study to provide safety data in patients with advanced stage DMD. The study focuses on safety assessments; however, because a majority of patients with advanced stage DMD are non-ambulatory,

The 96-week duration of the study provides sufficient follow-up time to obtain safety data in this population. The safety extension (not to exceed 48 weeks) will allow patients who have been receiving once weekly infusions of eteplirsen in Study 4658-204 to continue treatment until the product is commercially available or they are able to transition to another eteplirsen study.

8. SELECTION AND WITHDRAWAL OF PATIENTS

8.1. Number of Patients

Approximately 20 patients will be enrolled in this study.

8.2. Patient Inclusion Criteria

A patient must meet all of the following criteria to be eligible for this study.

- 1. Be a male with DMD with a mutation that may be amenable to exon 51 skipping (e.g., deletions of exons 45-50, 47-50, 48-50, 49-50, 50, 52, 52-63) as documented by a genetic report from an accredited laboratory confirming mutation endpoints by multiplex ligation-dependent probe amplification (MLPA) or sequencing.
- 2. Be between 7 and 21 years of age.
- 3. Has been on a stable dose of oral corticosteroids for at least 24 weeks prior to study drug administration and the dose is expected to remain constant (except for modifications to accommodate changes in weight) throughout the study, or has not received corticosteroids for at least 24 weeks prior to study drug administration and does not expect to start corticosteroids throughout the study.
- 4. **CCI**
- 5. Has a score of <4 on the Brooke Score for Arms and Shoulders.
- 6. Has cardiac and pulmonary function that, in the opinion of the investigator, is unlikely to decompensate over the study period.
- 7. Patients who are post-pubertal and sexually active must agree to use, for the entire duration of the study and for 90 days post last dose, a male condom and the female sexual partner must also use a medically acceptable form of birth control (e.g., oral contraceptives).
- 8. Able to understand and comply with all study requirements, in the Investigator's opinion, or if under the age of 18 years, must have a parent(s) or legal guardian(s) who is able to understand and comply with all the study requirements.
- 9. Willing to provide informed consent to participate in the study, or if under the age of 18 years, be willing to provide informed assent, if applicable, and have a parent(s) or legal guardian(s) who is willing to provide written informed consent for the patient to participate in the study.

8.3. Patient Exclusion Criteria

A patient who meets any of the following criteria will be excluded from this study.

- 1. Use of any pharmacologic treatment (other than corticosteroids) within 12 weeks of study drug administration that in the opinion of the Investigator might have an effect on muscle strength or function (e.g., growth hormone, anabolic steroids).
- 2. Previous treatment with SMT C1100/BMN 195 at any time.
- 3. Previous treatment with drisapersen (PRO051) within the last 6 months. Participation in any other DMD interventional clinical study within 12 weeks of study drug administration, or use of the shock training system or "STS," or planned use during this study. Concurrent participation in an interventional clinical study or observational trial is not permitted.
- 4. Major change in physiotherapy regimen within the past 3 months or expected change over the study period.
- 5. Major surgery within 3 months of study drug administration or planned major surgery for any time during this study.
- 6. Presence of other clinically significant illness including significant cardiac, pulmonary, hepatic, renal, hematologic, immunologic, behavioral disease or malignancy.
- 7. Systemic use of any aminoglycoside antibiotic within 12 weeks of study drug administration or anticipated need for use of an aminoglycoside antibiotic or statin during the study.
- 8. CCI
- 9. Must not require antiarrhythmic and/or antidiuretic therapy for heart failure. Patients are allowed to take other medication including angiotensin-converting enzyme (ACE) inhibitors, angiotensin receptor blocking agents (ARBs), β blockers or potassium, provided they have been on a stable dose for 24 weeks prior to study drug administration and the dose is expected to remain constant throughout the study.
- 10 **cc**
- 11. Prior or ongoing medical condition that could, in the Investigator's opinion, adversely affect the safety of the patient, make it unlikely that the course of treatment would be completed, or impair the assessment of study results.

8.4. Completion of a Patient's Participation in the Study

The length of a patient's participation may be from the time the informed consent form is signed up to Week 148 or up until the product is commercially available or until the patient transitions into a separate eteplirsen study.

8.5. Patient Withdrawal Criteria

Any patient can decide to withdraw from study participation at any time for any reason. In addition, the study Sponsor may decide to stop the study participation of any patient as deemed necessary. The Investigator may also stop the study participation of any patient at any time. Reasons for study withdrawal include but are not limited to:

- The patient was erroneously included in the study (i.e., was found to have not met the eligibility criteria).
- The patient experiences an intolerable or unacceptable AE.
- The patient is unable to comply with the requirements of the protocol.
- The patient participates in another investigational study without the prior written authorization of the Sponsor.

The Investigator or study staff will document the reason(s) for treatment discontinuation on the case report form (CRF).

Patients who received at least 1 dose of IP who discontinue from treatment within 4 weeks after a functional assessment visit will be asked to return for an End of Study visit within 4 weeks of their last visit. Patients who received at least one (1) dose of IP who discontinue treatment more than 4 weeks after a functional assessment visit will be asked to complete all Early Termination (Week 96) assessments within 30 days of discontinuation and a subsequent End of Study visit within 4 weeks of the Early Termination (ET) visit.

Following Week 96, patients may continue to receive eteplirsen for up to an additional 48 weeks and be followed as described in the Safety Extension portion of Section 2, Table 3 (Safety Extension Schedule of Events). They may receive weekly infusions of eteplirsen at the same dose, with continuous monitoring of adverse events and concomitant medications, while undergoing physical examination and safety laboratory assessments every 24 weeks. If patients discontinue eteplirsen during the Safety Extension, they will be asked to return for an End of Study visit 4 weeks after their final dose.

Patients who discontinue eteplirsen dosing in the Safety Extension Period in order to transition onto commercial drug or into a separate eteplirsen study do not require an End of Study visit.

8.6. Study Discontinuation

If the Sponsor, the Investigator, the medical monitor, the study monitor, institutional review board/independent ethics committee(s) (IRB/IEC), or appropriate regulatory officials discover conditions arising during the study that indicate the study should be halted or that the study center should be terminated, appropriate action may be taken after consultation among (at a minimum) the Sponsor, the Investigator, IRB/IEC and the medical monitor.

Conditions that may warrant termination of the study or an individual site include, but are not limited to, the following:

- The discovery of an unexpected, serious, or unacceptable risk to patients enrolled in the study
- A decision by the Sponsor to suspend or discontinue testing, evaluation, or development of the product
- Failure of the Investigator to enroll patients into the study at an acceptable rate
- Failure of the Investigator to comply with pertinent regulations of IRB/IEC or appropriate regulatory authorities
- Failure of the Investigator to comply with the protocol
- Submission of knowingly false information from the research facility to the Sponsor, the study monitor, IRB/IEC or regulatory authority
- Insufficient adherence to protocol requirements consistent with 21 CFR 312 or the European Clinical Trial Directive 2001/20/EC

Study termination and follow-up will be performed in compliance with the conditions set forth in International Conference on Harmonisation (ICH) E6 on Good Clinical Practice (GCP) as well as 21 CFR 312.56b and the European Clinical Trial Directive 2001/20/EC which require a Sponsor to ensure an Investigator's compliance with these requirements and to promptly secure a plan for compliance or discontinue shipments of the IP to the Investigator and end the Investigator's participation in the study.

9. TREATMENT OF PATIENTS

9.1. Investigational Product

Eteplirsen Injection

9.1.1. Packaging and Labeling

Please refer to the study-specific Pharmacy Manual for information on packaging and labeling.

The label text for the IP will at a minimum include the following information: product name/identifier, cautionary statement per 21 CFR 312.6, lot number (or alternative code), storage conditions, and the name of the Sponsor.

9.1.2. Storage

Vials of IP must be stored in a secured, limited-access area with appropriate temperature recording, controls, and monitoring. Details for IP handling, storage and for preparation of the diluted IP for administration can be found in the study specific Pharmacy Manual.

9.2. Treatments Administered

Eligible patients will receive a weekly IV infusion of 30-mg/kg dose of eteplirsen for 96 weeks, followed by a safety extension (not to exceed 48 weeks), until the product is commercially available or until patients can transition into a separate eteplirsen study.

The dose of eteplirsen will be calculated based on the most recent patient weight obtained at the site prior to the current visit. Eteplirsen should be prepared for dosing by following the steps detailed in the study-specific Pharmacy Manual.

Eteplirsen will be administered as an IV infusion over a period of approximately 35 to 60 minutes, or approximately 5 mL/min. It is recommended that a topical anesthetic cream (e.g., lidocaine 2.5%, prilocaine 2.5%, or LMX4 cream) be applied to the infusion site prior to each administration of eteplirsen. Additional administration and IP details are available in the study-specific Pharmacy Manual.

An implanted venous access port may be inserted for eteplirsen administration at the discretion of the Investigator. If eteplirsen is administered into an existing IV line, the line should be flushed with normal saline before and after administration of eteplirsen. After eteplirsen administration and the saline flush, the port may be flushed with heparin to heplock the port prior to removal of the infusion line.

No other medications may be administered concomitantly during the eteplirsen infusion.

All treated patients will be observed for at least 1 hour following the end of each eteplirsen infusion.

In-home study treatment administration by a visiting nurse may be available after Week 48.

The following guidelines for the timing of dosing should be followed throughout the study:

- 1. Patients should receive eteplirsen once every 7 days starting on Study Day 1. A window of ± 3 days from the scheduled dose is acceptable after the first infusion.
- 2. Patients may not receive 2 separate doses of eteplirsen within the same 60-hour period.
- 3. The medical monitor should be contacted in the event of ≥ 2 consecutive missed doses.

9.2.1. Dose Modification, Reduction, or Delay

There is no provision for dose alteration in this study. If a patient experiences an AE that requires interruption of administration of eteplirsen for ≥ 2 consecutive doses, the Investigator will consult with the Medical Monitor to determine whether the patient may resume treatment.

9.3. Randomization and Blinding

This is an open-label study, and therefore all patients will receive eteplirsen.

9.4. Prior and Concomitant Medications

The dosing regimen for oral corticosteroids for treatment of DMD including, but not limited to, prednisolone and prednisone, should be kept the same throughout the study.

The following therapies may be used before enrollment and throughout the study; however, the dosage should be constant throughout the treatment period, unless clinically indicated:

- Oral ACE inhibitors, including but not limited to perindopril and lisinopril
- Oral β-blockers, including but not limited to carvedilol and atenolol
- Angiotensin-receptor blockers, including but not limited to losartan, irbesartan, valsartan, and candesartan
- Oral laxatives, including but not limited to lactulose, Senokot, and Movicol
- Vitamin D and calcium supplements
- Alendronate (Fosamax) or other bisphosphonates used to treat osteoporosis/osteopenia by inhibiting osteoclasts
- Over-the-counter herbal preparations, including herbal supplements, vitamins, minerals, and homeopathic preparations, provided the patient had been on stable doses for 24 weeks before enrollment in this study

Other concomitant medications (e.g., vitamins or other non-RNA antisense medications) may also be taken if, in the opinion of the Investigator, they do not interfere with study assessments and outcomes. The Investigator should contact the Medical Monitor if he/she is unsure of the impact of a concomitant medication on study assessments and outcomes. Every attempt should be made to keep the dosage constant throughout the study period (i.e., through Week 96); although modifications to accommodate changes in weight are permitted.

Introduction of new physiotherapy interventions during the course of the study must be avoided unless the best interests of the patient are at risk. Should a contracture develop during the course

of the study, and it is considered in the best interest of the patient to treat the contracture, then any of the following interventions may be used to reduce the contracture, but they must be clearly documented:

- Contracture control devices
- Night splints
- Stretching exercises (passive, active, self)
- Serial casting

The following therapies are **not permitted** during the conduct of this study:

- Systemic or oral steroids for non-DMD conditions
- Investigational agents for the treatment of DMD
- Any medication with the potential to affect muscle mass, strength, and/or function, such as, but not limited to, growth hormone and PDE-5 inhibitors
- Immunosuppressants (other than oral or systemic corticosteroids, as outlined)
- Systemic aminoglycoside antibiotics (unless discussed and agreed upon with the Investigator and the Medical Monitor)
- Statins (unless discussed and agreed upon with the Investigator and Medical Monitor)

9.5. Treatment Compliance

Treatment compliance will be assessed via compliance with scheduled weekly infusions.

10. STUDY ASSESSMENTS

10.1. Study Schedule of Events

A detailed schedule of the study assessments and times is shown in Section 2.

10.2. Assessments at the Screening/Baseline Visits

10.2.1. Informed Consent

Written informed consent from the patient or parent/legal guardian(s) and assent from the patient (if applicable) to participate in this study must be obtained prior to beginning any of the procedures for this study.

10.2.2. Medical History

Medical history will be obtained for all patients.

10.2.3. Blood samples for DMD Genotyping and CC

Blood samples will be obtained at Screening for confirmation of DMD genotyping. Patients may start dosing based on local genotyping results provided that these results fulfill the required criteria described in Section 8.2; however, all patients must undergo genetic testing to confirm the exon 51 skippable mutation. Patients whose genotype is not confirmed to be exon 51 skippable will be excluded from continuing in this trial.

10.3. Safety Assessments

10.3.1. Physical Examination

Physical examinations, full and brief, will be conducted at the time points specified in Section 2. Physical examinations will be performed by the Investigator, a physician Sub-Investigator, or a Nurse Practitioner (if licensed in the state or province to perform physical examinations). Full physical examinations will include examination of general appearance; head, ears, eyes nose, and throat (HEENT); heart; lungs; chest; abdomen; skin; lymph nodes; musculoskeletal; and neurological systems. Brief physical examinations will include examination of general appearance, HEENT, heart, lungs, chest, abdomen, and skin.

10.3.2. Vital Signs and Weight

Vital signs (blood pressure, heart rate, respiration, and oral temperature) and weight will be measured at the time points specified in Section 2.

For infusion visits, vital signs are to be collected within approximately 30 minutes prior to infusion and approximately 5, 30, and 60 minutes after the end of the infusion. If the patient has not experienced an infusion reaction after the first year of treatment, vital signs may be collected only 30 minutes after the end of the infusion. All assessments will be performed after patients have remained seated for 5 minutes. Pulse rate and respiratory rate should be measured over 1 minute

Details about how weight measurements are obtained are provided in the Clinical Evaluator Manual. If a patient's weight varies by more than 10% from the prior visit, the patient should be re-weighed to confirm the result, and an explanation of the change should be documented.

10.3.3. Clinical Laboratory Evaluations

The following routine clinical laboratory tests will be collected at the time points specified in Section 2 and analyzed by an accredited central laboratory selected by the Sponsor and prepared according to the Laboratory Manual provided for the study:

Chemistry: Sodium, chloride, potassium, calcium, glucose, creatinine, blood urea

nitrogen (BUN), albumin, uric acid, total bilirubin, alkaline phosphatase, amylase, alanine aminotransferase (ALT), aspartate aminotransferase (AST), gamma-glutamyl transferase (GGT), lactase dehydrogenase (LDH), C-reactive protein (CRP), creatine kinase

(CK), and serum cystatin C

Hematology: Red blood cells (RBCs), total white blood cells (WBCs), hemoglobin,

hematocrit, neutrophils, lymphocytes, monocytes, eosinophils,

basophils, platelets, and abnormal cells

Coagulation Screen: Prothrombin time, International Normalized Ratio (INR), and

activated partial thromboplastin time (aPTT)

Urinalysis: pH, specific gravity, protein, glucose, ketones, cytology, hemoglobin,

and kidney injury molecule-1 (KIM-1)

Any value outside of the current reference ranges for the laboratory performing the test will be flagged on the laboratory results. The Investigator will determine whether abnormal assessment results are clinically significant (CS) or not clinically significant (NCS). Clinical significance is defined as any variation in assessment results that has medical relevance resulting in an alteration in medical care. If clinically significant deterioration from baseline levels is noted, the Investigator will continue to monitor the patient with additional assessments until:

- Values have reached normal range and/or baseline levels; or
- In the judgment of the Investigator together with the Sponsor's Medical Monitor, abnormal values assessed to be not related to the administration of investigational

product or other protocol-specific procedures, and additional assessments are not medically indicated.

10.3.4. Height and Ulnar Length

Height and ulnar length will be measured at the time points specified in Section 2.

Height should be measured with shoes off. If standing height cannot be obtained, height should be calculated using the following equation (Gauld 2004):

Height (cm) =
$$4.605U + 1.308A + 28.003$$

where U is length of the ulna measured using an anthropometer or callipers, and A is patient's age (years).

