6.2. Exploratory Objectives

7. INVESTIGATIONAL PLAN

7.1. Overall Study Design

This is an open-label, multicenter study to explore the safety and tolerability of eteplirsen injection in approximately 20 patients with advanced stage DMD with confirmed genetic mutations amenable to treatment by exon 51 skipping.

Patients will be evaluated for inclusion during a Screening/Baseline period of up to 4 weeks. Written informed consent from the patient and/or parent/legal guardian and assent, if applicable, to participate in the study must be obtained prior to beginning any study-related procedures.

- Once eligibility is confirmed, patients will undergo Screening Assessments as indicated in Section 2 (Schedule of Events).
- Blood samples collected at the Screening Visit for the safety lab assessments must be obtained within 2 weeks prior to the Baseline/Week 1 visit, and results must be available prior to dosing at Baseline/Week 1.
 - However, if more than 2 weeks have elapsed since the collection of blood samples for the Screening safety lab assessments, it must be repeated.
 - If less than 2 weeks have elapsed since the collection of blood samples for the Screening safety lab assessments, additional safety lab assessments do not need to be performed, and the patient may proceed with Baseline/Week 1 assessments as indicated in Section 2.

Starting at Week 1, enrolled patients will receive once weekly IV infusions of 30 mg/kg eteplirsen for 96 weeks, followed by a safety extension (not to exceed 48 weeks), until the product is commercially available or until patients can transition into a separate eteplirsen study.

Safety will be regularly assessed throughout the study via the collection of AEs, laboratory tests, electrocardiograms (ECGs), echocardiograms (ECHOs), vital signs, and physical examinations.

C

Following the end of the weekly infusions, patients will be required to return to the study site for End of Study on-treatment safety evaluations.

The total duration including Screening, Treatment, Safety Extension, and End of Study Follow-up periods is approximately 148 weeks. The Safety Extension will start following completion of the Week 96 visit and is not to exceed 48 weeks. Dosing in the Safety Extension will continue until product is commercially available or until patients can transition into another study to receive eteplirsen.

Refer to Section 10 for the detailed list of study assessments.

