13.8.2.2. Physical Examination, Vital Signs, Weight, and Height/Ulnar Length

Vital signs, weight, and height/ulnar length will be presented by treatment condition and visit, summarizing the actual values and change from Baseline to each visit for each parameter using descriptive statistics. Frequency tables of predefined change abnormal in vital sign values will be generated.

Results from physical examinations will be presented in patient data listings.

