4.4.2 Demographics and Baseline Characteristics

- Age, race, ethnicity, weight, height, body mass index (BMI), genotype for column ambulatory status, and column will be summarized.
- Age will be calculated at date of first dose of eteplirsen at the Week 1 visit
- For the purposes of the demographic summaries, weight will be the last available measurement taken before the first study drug administration.
- BMI will be calculated as BMI = Weight (kg) / Height (m)². Any measurements in other units will be converted to kilograms and meters prior to the calculation. Weight (kg) = weight (lb)/2.2. Height (m) = height (inches)*0.0254.

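### For patients who cannot stand, the height-change rows will show about 2.4 cm of growth by Week 96 even when the ulna has not grown

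*Protocol*

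**What the plan says.** Protocol 10.3.4 gives two routes to a height. Standing height is measured with shoes off. Otherwise, "If standing height cannot be obtained, height should be calculated using the following equation": height in cm is "4.605U + 1.308A + 28.003", where U is ulnar length and "A is patient's age (years". Neither document sets an upper age for A or says whether it is decimal or completed years.

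Inclusion criterion 2 (Protocol 8.2) is "Be between 7 and 21 years of age". Protocol 7.4 notes that "a majority of patients with advanced stage DMD are non-ambulatory"; the rest of that sentence is not visible and no number is given.

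The schedules in both documents place height and ulnar length at Screening, Baseline/Week 1 and Weeks 12, 24, 36, 48, 72 and 96 (or early termination). Neither is scheduled in the Safety Extension.

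Protocol 13.8.2.2 presents vital signs, weight and height/ulnar length by visit, "summarizing the actual values and change from Baseline to each visit for each parameter using descriptive statistics". The SAP does not mention the equation and has no section on height change. It uses height in the demographic summary, where "BMI will be calculated as BMI = Weight (kg) / Height (m)²" (SAP 4.4.2). SAP Section 6 lists one change from the protocol's analyses, on Holter monitoring, so the height summary is not expressly withdrawn.

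**The concern.** In the equation, age raises predicted height at a fixed rate whatever the ulna does. That is tolerable for a single estimate of stature. It causes trouble when the same equation is applied repeatedly to one patient and the results are subtracted, because the elapsed time then appears in the table as growth. In a patient whose ulna is not growing, the whole of the reported change comes from the age term. The error always has the same sign and increases with each visit, so averaging over patients does not remove it.

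There is a second problem that does not depend on when growth stops. The choice between measured and calculated height is made at each measurement. Protocol 5.1 says most patients lose the ability to walk at 10 to 14 years, which is inside the eligible range, and SAP 5.5.7.1 splits adverse event tables by Baseline ambulatory status, so ambulatory patients are expected. Some may stand at Baseline and not later. Their change score would mix true change with the difference between two methods, and neither document asks for a consistent method or a method flag.

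At stake is whether the height-change rows can be read as growth. Protocol 5.1 names growth inhibition as a side effect of corticosteroids, and criterion 3 allows patients on a stable oral dose, so some readers will look at those rows with that question in mind.

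**Working it through.** The documents give no figure for this effect, so there is nothing to reproduce. The check is arithmetic on the protocol's own equation.

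**Inputs**
- Coefficients (Protocol 10.3.4): 4.605 cm per cm of ulna; 1.308 cm per year of age; constant 28.003 cm.
- Time (Protocol 7.1): "Starting at Week 1, enrolled patients will receive once weekly IV infusions of 30 mg/kg eteplirsen for 96 weeks". From Week 1 to Week 96 is nominally 95 elapsed weeks; a full 96 weeks is shown as the alternative.
- Assumption: change in U is 0, meaning a patient whose ulna is not growing. The documents give no growth data and no age at which growth stops.

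**Formula**

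Change in calculated height = 4.605 × (change in U) + 1.308 × (change in A). With change in U = 0 this is 1.308 × elapsed weeks × 7/365.25. Starting age and ulnar length cancel.

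**Decimal age**

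| Visit | Elapsed weeks | Apparent growth (cm) |
|---|---|---|
| Week 12 | 11 | 0.28 |
| Week 24 | 23 | 0.58 |
| Week 36 | 35 | 0.88 |
| Week 48 | 47 | 1.18 |
| Week 72 | 71 | 1.78 |
| Week 96 | 95 | 2.38 |

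At Week 96: 95 × 7/365.25 = 1.821 years, and 1.308 × 1.821 = 2.38 cm. With 96 full weeks: 1.840 years and 2.41 cm.

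**Completed years**

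A patient passes one or two birthdays in 1.821 years, so apparent growth is 1.308 cm or 2 × 1.308 = 2.616 cm. If birthdays are evenly spread, about 82% pass two, and the mean is 1.308 × 1.821 = 2.38 cm. The 2.4 cm is therefore each patient's value with decimal age, but only the group mean with completed years.

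**Scale**

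2.38 / 4.605 = 0.52 cm. The age term adds as much calculated height as a real ulnar gain of about half a centimetre.

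**Method switch**

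For a patient measured at Baseline and calculated later, change = (calculated height at the visit) − (standing height at Baseline). This contains the equation's prediction error for that patient as well as any growth. The documents give no prediction error, so no size can be attached.

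**The case against.** The strongest reply is that little depends on these rows. Height is not among the safety endpoints in Protocol 7.3.1, dose is calculated from weight (Protocol 9.2), BMI is listed only as a baseline characteristic, and no visible threshold or test uses height. The study has one arm, about 20 patients and descriptive safety analyses. All of this stands, and it makes the point minor.

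A second reply is that ulnar length is already measured at the same visits and named in the same summary. This also stands. A reader might infer that the age term would hide a growth-inhibition signal. The documents do not support that, because a flat ulna would show in the companion rows. The height rows would still be wrong and would disagree with those rows without explanation.

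Third, the SAP specifies no height-change table, and Protocol 13.1 leaves full details to the SAP. Whether the table will be produced is therefore not certain. It is committed to in the protocol and not withdrawn in SAP Section 6, which is reason enough to settle it in wording.

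Fourth, the extent is unknown. The remark about non-ambulatory patients concerns advanced-stage disease in general, part of the eligibility criteria is not visible, and nothing says how many patients will be unable to stand and have stopped growing.

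A reader might also infer that baseline BMI is biased low in older patients. As an illustration, take an ulna of 25 cm: calculated height is 4.605 × 25 + 28.003 + 1.308 × 16 = 164.06 cm at age 16 and 170.60 cm at age 21. If growth ended at 16 and the equation were exact at that age, height at 21 would be 6.5 cm too high and BMI about 7.5% too low, since (164.06/170.60)² = 0.925. If growth ended at 18 (166.67 cm), the figures are 3.9 cm and about 4.6%. The ulnar length, the stopping age and the equation's accuracy at that age are all absent from the documents, so the bias is conditional and cannot be asserted.

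**Conclusion.** The point holds, as a minor one. As written, the plan calculates height with an unlimited age term, admits patients up to 21 and summarises change from Baseline. In a patient with a constant ulna and no standing height, the table would show about 2.4 cm of growth by Week 96 (1.3 or 2.6 cm with completed years) when the ulna shows none. A patient who loses the ability to stand during the study would have a change score built from two different methods.

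The 2.4 cm rests on the protocol's coefficient, the visit schedule and the premise that the ulna does not change. It does not depend on starting age or ulnar length. How many patients meet the premise cannot be determined.

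The effect stays within the descriptive height-change rows. The documents do not support extending it to the safety endpoints, to dosing, or to a definite bias in baseline BMI.

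**What to change.** In Protocol 13.8.2.2 and the SAP:

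- Tabulate change from Baseline in height only for visits where standing height was measured both at Baseline and at that visit.
- For patients with calculated height, use the change in ulnar length as the growth summary, and do not tabulate change in calculated height.
- Flag each height as measured or calculated in the listing and in the baseline height and BMI summary.

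Two other remedies may come to mind and are not recommended. Holding A at its Baseline value would give 0 for a constant ulna, but in boys who are still growing it would remove about 2.4 cm of growth that the equation is meant to predict. Capping A at a chosen age needs a value that the documents do not supply.

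The cost is wording, with no new visit or measurement. The flag needs the method to be on record; the documents do not show whether the case report form captures it. The downside is that fewer patients contribute to the height-change rows.
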